THE IMPACT OF INTRAOPERATIVE LIDOCAINE INFUSION ON POSTOPERATIVE RECOVERY AFTER HYSTEROSCOPY: A RANDOMIZED CONTROLLED TRIAL

[name].

Afyonkarahisar University of Health Sciences

Medical School Hospital

Department of Obstetrics and Gynecology

November 2024

Supervisor: Assistant [name] [name]

Introduction: Hysteroscopy is a surgical method which is frequently used for the diagnosis and treatment of intrauterine pathologies including adhesions, polyps and endometrial hyperplasia. This procedure can be performed at the office without anesthesia or at the surgery room under anesthesia.

Purpose: This study aims to investigate the efficiency of intraoperative lidocaine infusion, which is frequently preferred for surgical procedures, in reducing postoperative pain, nausea, and vomiting, as well as the need for opioid analgesics and anti-emetics.

Methods: This is a prospective review of 150 patients who have consecutively undergone elective hysteroscopy for various indications. The patients aged <18 years and >65 years, the patients with body mass indices $< 18.5 \text{ kg/m}^2$ or $\geq 25 \text{ kg/m}^2$, the patients with American Society of Anesthesiologists physical status $>\text{II}$, the patients with a history of allergy to local anesthetics, the patients with chronic pain syndromes, the patients who had long-term analgesic and sedative use, the patients with opioid dependence, and the patients severe arrhythmia, organic heart disease, and mental or neurological disorders were excluded.

The participants were randomly assigned to the study group (lidocaine) or the control group (saline) using a computer-generated randomization sequence. Thus, 75 patients were allocated to either research or control groups. The patients in the research group received 1% intravenous lidocaine at a dose of 0.15 ml/kg before the initiation of general anesthesia and the infusion of 1% lidocaine would be continued at a dose of

0.2 ml/kg/hour throughout the procedure. In the control group, 0.9% saline solution would be used instead of lidocaine. Both the patients and the healthcare providers administering the interventions were blinded to the allocation.

The primary endpoint was the postoperative pain assessed by Visual Analog Scale (VAS) at 30th minute, 60th minute, 4th hour, and 24th hour. Secondary endpoints included nausea, vomiting, need for analgesic and anti-emetic drugs during the postoperative period.

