**STATISTICAL ANALYSIS PLAN**

**24th DECEMBER 2024**

**STATISTICAL ANALYSIS PLAN**

Collected data were analyzed using Statistical Package for Social Sciences version 25.0 (SPSS, IBM Armonk, NY, USA). Kolmogorov-Smirnov test was used to test data distribution. Continuous variables were expressed as mean  $\pm$  standard deviation and categorical variables were presented as frequencies and percentages where appropriate. Student's t-test was used to compare the continuous variables of the study and control groups whereas chi-square test was used to compare the categorical variables of the study and control groups. Two-tailed p values less than 0.05 were accepted as statistically significant.

A post hoc analysis was carried out to make a retrospective power analysis and it was determined that a cohort size of 150 women (75 patients in the study group and 75 patients in the control group) had 87.6 % power to detect a difference at the 0.05 significance level.

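### Primary VAS pain endpoint has four time points but no primary time, success rule or multiplicity adjustment; if any one time counts, the false-positive chance is about 9–19%, not 5%

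*Protocol*

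**What the plan says.** In the Methods section of the protocol, the primary endpoint is pain score at four times: "The primary endpoint was the postoperative pain assessed by Visual Analog Scale (VAS) at 30th minute, 60th minute, 4th hour, and 24th hour". The section gives no primary time, summary measure, testing order or required number of positive times.

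The text reviewed from the SAP does not mention VAS or any time point. Two general rules in its first paragraph apply by default: "Student's t-test was used to compare the continuous variables of the study and control groups" and "Two-tailed p values less than 0.05 were accepted as statistically significant". It contains no repeated-measures model, joint test or multiplicity adjustment. The second paragraph reports a retrospective calculation that 75 women per arm "had 87.6 % power to detect a difference at the 0.05 significance level". It does not say for which endpoint, time or effect size.

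**The concern.** Read together, the two documents give four between-group t-tests on the primary endpoint, each judged at 0.05, and no statement of what makes the trial positive. Nothing prevents a p value below 0.05 at one time, with the other three null, from being reported as a positive primary result. Under that reading the chance of a false primary claim is above 5%. Under the opposite reading, with all four times required, it is well below 5% and power falls.

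The choice may also still be open after the results are known. The SAP is written in the past tense ("Collected data were analyzed using Statistical Package for Social Sciences version 25.0") and its power analysis is retrospective, so the data may have been seen before any rule was fixed.

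**Working it through.** **Inputs.** Four VAS times (protocol, Methods). Two-sided 0.05 and Student's t-test (SAP, first paragraph). 75 women per arm and 87.6% power (SAP, second paragraph). The correlation of VAS between times is not given. It is assumed here to range from 0 to 0.9 and to be equal for all pairs, with a first-order autoregressive pattern, AR(1), as a check.

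**The plan's own figure.** The 87.6% cannot be reproduced, because no effect size, SD or endpoint is stated. It can only be solved backwards. With the normal approximation, d = (1.960 + 1.155) × √(2/75) = 0.509 SD. With the noncentral t distribution, d = 0.512. The error rates below do not depend on this figure.

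**Any-time rule, no true effect.** For independent tests, 1 − 0.95⁴ = 0.1855. For equal correlation ρ and c = 1.96, the chance of at least one significant result is

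1 − ∫ [Φ((c − √ρ·u)/√(1−ρ)) − Φ((−c − √ρ·u)/√(1−ρ))]⁴ φ(u) du.

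Counting only results that favour lidocaine, the independent case is 1 − 0.975⁴ = 0.0963, against a nominal 2.5%.

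**All-four rule.** The chance that all four are significant in the same direction is

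2 ∫ [1 − Φ((c − √ρ·u)/√(1−ρ))]⁴ φ(u) du.

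**Holm.** With no effect at any time, a false claim requires the smallest p to fall below 0.05/4 = 0.0125. For independent tests this is 1 − 0.9875⁴ = 0.0491.

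| ρ | Any of four, equal ρ | Any of four, AR(1) | Any of four, favouring lidocaine | All four | Holm, any time |
|---|---|---|---|---|---|
| 0 | 18.5% | 18.5% | 9.6% | <0.1% | 4.9% |
| 0.5 | 15.6% | 16.6% | 7.8% | 0.1% | 4.3% |
| 0.7 | 13.0% | 14.3% | 6.5% | 0.6% | 3.7% |
| 0.8 | 11.4% | 12.7% | 5.7% | 1.0% | 3.2% |
| 0.9 | 9.4% | 10.4% | 4.7% | 1.9% | 2.6% |

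The AR(1) column comes from simulation. All columns except AR(1) and Holm use equal correlation and agree between the formulas and simulation to within about 0.1 percentage point; the Holm column also uses equal correlation. Beyond the table, the any-time rate with equal correlation is 8.0% at ρ = 0.95 and 6.3% at ρ = 0.99.

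**Power, for illustration only.** Suppose the 87.6% applied to each VAS test and the same effect (0.512 SD) were present at all four times. The unadjusted power to win at every time would be 0.876⁴ = 0.589 if independent and about 80% at ρ = 0.9 (simulated). The power at a single time, tested at Holm's strictest level of 0.0125, would be 73%. Averaged over Holm's steps, the per-time power would be about 84% (ρ = 0) to 79% (ρ = 0.9).

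**The case against.** Neither document states an any-time rule, so what is proven is an unspecified rule, not a demonstrated inflation. That is right, and the 9–19% is conditional for this reason. The omission is still a defect, because the any-time reading is fully compatible with the text.

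The upper end needs independence, which is implausible for pain scores from the same patients within 24 hours, and at correlations above 0.9 the rate drops below 9%. Both points are fair. The rate nevertheless exceeds 5% at any correlation below 1, and at 0.9 it is still nearly double the nominal level.

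The rates count significance in either direction, whereas the trial's purpose is to reduce pain. The chance of a false claim of benefit is about half as large, 9.6% to 4.7%. Its proper comparator is then 2.5%, so the inflation is still roughly 2 to 4 times.

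The power figures rest on a retrospective 87.6% that is tied to no endpoint. They are therefore only illustrative, and the conclusion does not need them.

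Holm is not the only valid remedy. One primary time, a fixed testing order or a summary measure would each serve if chosen before the data were seen. If the data have been seen, no wording restores prespecification. This stands, and it affects how the fix must be reported. Finally, part of the SAP file was not in the text reviewed, so statements about what the SAP omits refer to the text supplied.

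**Conclusion.** The concern holds and must be fixed. The plan as written gives four unadjusted primary tests and no success rule. The false-positive rate of the primary claim then runs from 1.9% or less (all four required) to between 9.4% and 18.5% (any one sufficient), for correlations between 0 and 0.9. The size depends on that assumed correlation and on which rule is applied. The absence of a rule depends on neither. Confidence is high.

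**What to change.** Add to the SAP, in words such as: *The four between-group t-tests on VAS pain (30 min, 60 min, 4 h, 24 h) are adjusted by the Holm method at an overall two-sided level of 0.05. A primary effect is claimed only at times with a Holm-adjusted p below 0.05. All four raw and adjusted p values are reported.* If any results have been seen, state that the adjustment was added afterwards.

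Holm suits this trial because it is valid under any correlation, keeps all four times and requires no favoured time to be chosen late.

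The cost is SAP wording and a hand adjustment of four p values, with no new data. The downside is that an isolated p between 0.0125 and 0.05 may no longer support a claim, with the illustrative loss of per-time power shown above. If the data are already known, the change protects the reporting but cannot restore prespecification.

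### Does the plan need a rule for pain scores recorded after an analgesic, and a single definition of analgesic need?

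*Protocol*

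**What the plan says.** The Protocol's Methods section sets the primary endpoint: "The primary endpoint was the postoperative pain assessed by Visual Analog Scale (VAS) at 30th minute, 60th minute, 4th hour, and 24th hour". It continues: "Secondary endpoints included nausea, vomiting, need for analgesic and anti-emetic drugs during the postoperative period". The Purpose section describes the aim as efficacy "in reducing postoperative pain, nausea, and vomiting, as well as the need for opioid analgesics and anti-emetics". The first of these two descriptions covers analgesics of any kind and the second only opioids. Neither says whether need is a yes/no item, a count or a dose. On group size, Methods reports that "75 patients were allocated to either research or control groups", and the SAP's power paragraph confirms 75 in each arm.

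The SAP assigns tests by type of variable. For VAS, the operative words are "t-test was used to compare the continuous variables of the study and control groups". For yes/no items they are "chi-square test was used to compare the categorical variables of the study and control groups", and the same paragraph has categorical variables shown as frequencies and percentages. Nothing in the available text excludes, replaces or adjusts a score because an analgesic was given. The SAP is written in the past tense ("Collected data were analyzed using Statistical Package for Social Sciences version 25.0"), which suggests that the data were already in hand.

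**The concern.** Analgesics given after surgery sit between the infusion and the later pain scores. Suppose lidocaine works and control patients therefore take more analgesic. Their later scores then fall and the VAS difference narrows. A small VAS difference with heavier analgesic use in controls is a different finding from a small difference with equal use. A plan that makes VAS primary might be expected to say which comparison it intends, and to define analgesic need tightly enough for the two results to be read together.

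The two descriptions of need add to the doubt. If only opioids were counted, use of other analgesics would go unseen. The missing measure also seems to leave open whether the t-test or the chi-square test applies. At stake would be the interpretation of a small or null VAS result, and some freedom in how one secondary endpoint is built.

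**Working it through.** **1. The plan's own figure.** The SAP reports 87.6% power for 75 per arm at 0.05 but names no endpoint, effect, standard deviation or rates, so the figure cannot be reproduced forwards. Solved backwards for two means (two-sided, normal approximation), it implies a standardised difference of (1.960 + 1.155)/√(75/2) = 3.115/6.124 = 0.509. Stating how scores after an analgesic are handled would change neither the sample size nor the significance level, so this figure does not bear on the point.

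**2. What the VAS analysis does as written.** The input is every recorded score, the test is a t-test between arms, and no score is dropped for analgesic use. The result is the difference in mean pain whatever analgesic was taken. A sentence saying so would describe the same calculation.

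**3. How far unequal use could move the VAS difference (assumed values only).** Start from 0.509 SD and let an analgesic lower VAS by g SD. The observed difference is then 0.509 − g × (control use − lidocaine use).

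| Excess use in controls | g = 0.5 | g = 1.0 |
|---|---|---|
| 0 points | 0.509 (power 87.6%) | 0.509 (87.6%) |
| 20 points | 0.409 (70.7%) | 0.309 (47.3%) |
| 30 points | 0.359 (59.4%) | 0.209 (24.8%) |

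The movement is towards zero. It is part of what pain under usual analgesic care means, and writing down the default would not alter any cell. The documents give no rates or analgesic effect, so the table shows direction and does not estimate this trial.

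**4. Precision of the analgesic comparison, if need is yes/no.** With n = 75 per arm and equal observed use p, the 95% half-width is 1.96 × √(2p(1 − p)/75).

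- p = 0.20: 1.96 × √(0.32/75) = 12.8 points
- p = 0.30: 1.96 × √(0.42/75) = 14.7 points
- p = 0.50: 1.96 × √(0.50/75) = 16.0 points

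Power comes from full enumeration of two binomials of size 75, with the uncorrected Pearson chi-square test at two-sided 0.05. Control rates are assumed.

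| Control use | Power, 10 points lower on lidocaine | Power, 15 points lower | Difference for 80% power |
|---|---|---|---|
| 20% | 41% | 83% | 14.6 points |
| 30% | 29% | 60% | 18.2 points |
| 40% | 25% | 50% | 20.7 points |
| 50% | 25% | 48% | 21.9 points |
| 60% | 25% | 47% | 22.4 points |

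With a continuity correction, power for 10 points falls to 32/23/20/20/20%. These figures describe the limits of a secondary comparison at this sample size. They would be the same however need was worded, provided it is yes/no with the same rates.

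**5. The two descriptions side by side.** The Purpose is a one-sentence aim; the endpoint list in Methods says what is to be compared. Opioids are analgesics, so counting all analgesics includes them and the two statements can stand together. The measure is open, but the SAP's rule by variable type covers either form: a yes/no record goes to frequencies and chi-square, and a dose or count goes to mean, standard deviation and t-test.

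**The case for a change.** The strongest case for a change is that it would be cheap and would close a real gap. Reducing analgesic need is one of the trial's own aims, so unequal use is something the investigators hope to see. Readers of a small VAS difference would then need analgesic use beside it, defined once. As written, someone could choose between opioids and all analgesics, or between yes/no and dose, after seeing the data. A difference with a 95% interval would also say more than a p-value, given the widths above.

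Part of this stands. The scope and measure of analgesic need are loosely worded, and an interval is better reporting. The rest does not call for an amendment. The VAS comparison is unaltered by stating its default. The warning about a non-significant chi-square answers a misreading that neither document makes. Counts by arm are already provided for if need is yes/no. A split by time of analgesic depends on chart detail that the documents do not mention. If the data are already collected, a definition written now would itself be post hoc and could not restore prespecification. The effect in step 3 also runs one way: if controls use more analgesic, the VAS difference shrinks, so a positive lidocaine result is not undermined by this route.

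**Conclusion.** No change to the plan follows. The gap is missing detail that an analyst would fill sensibly: recorded scores are compared as they stand, analgesic need is taken from the endpoint list, and the test follows from how need was recorded. Carrying out the SAP as written gives no wrong VAS result, and the documents hold nothing from which an effect on that result could be sized.

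What remains is the loose scope and measure of one secondary endpoint. As a matter of reading the results, a non-significant comparison of analgesic use at 75 per arm would leave differences of about 13 to 16 points open if use is equal at 20% to 50%.

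This rests on three assumptions: all recorded VAS scores enter the t-test, as the absence of any exclusion rule implies; need is recorded as yes/no wherever the chi-square figures are used; and the control rates, which the documents do not give, lie in the range shown.

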**STATISTICAL ANALYSIS PLAN**

**24th DECEMBER 2024**

**STATISTICAL ANALYSIS PLAN**

Collected data were analyzed using Statistical Package for Social Sciences version 25.0 (SPSS, IBM Armonk, NY, USA). Kolmogorov-Smirnov test was used to test data distribution. Continuous variables were expressed as mean  $\pm$  standard deviation and categorical variables were presented as frequencies and percentages where appropriate. Student's t-test was used to compare the continuous variables of the study and control groups whereas chi-square test was used to compare the categorical variables of the study and control groups. Two-tailed p values less than 0.05 were accepted as statistically significant.

A post hoc analysis was carried out to make a retrospective power analysis and it was determined that a cohort size of 150 women (75 patients in the study group and 75 patients in the control group) had 87.6 % power to detect a difference at the 0.05 significance level.

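### Is it a flaw that pain scores from mixed hysteroscopy indications are compared with a t-test that adjusts for no baseline covariate?

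*SAP*

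**What the plan says.** The SAP has one rule for continuous outcomes: Student's "t-test was used to compare the continuous variables of the study and control groups". It mentions no covariate, regression model or stratified comparison. VAS is not named there; it comes under this rule because the protocol's primary endpoint is a pain score at four postoperative times. The significance rule is "Two-tailed p values less than 0.05 were accepted as statistically significant".

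The protocol's Methods describe "150 patients who have consecutively undergone elective hysteroscopy for various indications", and its Introduction says hysteroscopy is used for "intrauterine pathologies including adhesions, polyps and endometrial hyperplasia". On allocation it says: "The participants were randomly assigned to the study group (lidocaine) or the control group (saline) using a computer-generated randomization sequence". No stratification factor is given. Age, BMI and ASA class are eligibility criteria, so they must be known before allocation. No preoperative VAS is mentioned, and nothing says that indication is recorded for use in the analysis.

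On timing, the SAP is in the past tense ("Collected data were analyzed using Statistical Package for Social Sciences version 25.0") and closes with a power statement: "A post hoc analysis was carried out to make a retrospective power analysis". It puts that power at 87.6% with 75 women per arm.

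**The concern.** Pain may well differ between indications or between the procedures they lead to. If neither the randomisation nor the analysis accounts for this, the variation between indications stays in the error term of the t-test. Adjusting for prognostic baseline variables is a standard way to recover that precision. It needs no extra patients, only a sentence in the SAP and one linear model per VAS time. Pooled indications, no stratification and no covariates together therefore look like a missed step.

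What would be at stake is the width of the confidence interval and a few points of power. Some readers may also suspect that pooling unlike patients makes the t-test itself unreliable.

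**Working it through.** **Inputs.** From the SAP: 75 per arm, two-sided 0.05, power 87.6%. Not in the documents, and therefore assumed: the share R² of VAS variance that covariates explain (shown from 0 to 0.25) and the number of covariate degrees of freedom k. Here k = 2 stands for age plus ASA class; k = 3, 4 or 5 adds indication at two, three or four levels.

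**The plan's own figure.** The 87.6% cannot be reproduced, because the SAP gives no effect size, SD or endpoint for it. It can only be solved backwards. By the normal approximation, d = (1.960 + 1.155) × √(2/75) = 3.115 × 0.1633 = 0.509 SD; with the noncentral t on 148 df, d = 0.512 SD. This value serves below only as an illustration.

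**Step 1: is the unadjusted test valid?** The simulation used three equally likely indication groups, unstratified 75:75 allocation, no treatment effect and 10,000 runs per case (Monte Carlo standard error about 0.002).

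| Variance explained by indication | Type I error, unadjusted t-test |
|---|---|
| 0% | 0.054 |
| 10% | 0.050 |
| 25% | 0.049 |

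Pooling indications does not inflate the error rate. The protocol is very short, so its silence does not prove that allocation was unstratified. Had it been stratified by indication, the same test would be conservative: 0.037 at R² = 0.10 and 0.024 at R² = 0.25. That costs power but does not produce false positives.

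**Step 2: what would adjustment change?** The squared standard error in SD units is (1 − R²) × (2/75) × VIF, with VIF = 147/(147 − k) and 148 − k residual df. VIF is 147/145 = 1.0138 for k = 2 and 147/142 = 1.0352 for k = 5. Adjustment gains only if (1 − R²) × VIF falls below 1, apart from a very small change in the t quantile. Break-even R² is 0.0138, 0.0207, 0.0276 and 0.0345 for k = 2, 3, 4 and 5.

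| | R² = 0 | R² = 0.05 | R² = 0.10 | R² = 0.20 |
|---|---|---|---|---|
| Change in 95% CI half-width, k = 2 | +0.7% | −1.9% | −4.5% | −9.9% |
| Change in 95% CI half-width, k = 5 | +1.8% | −0.8% | −3.5% | −9.0% |
| Power at d = 0.512, k = 2 | 87.2% | 88.8% | 90.3% | 93.3% |
| Power at d = 0.512, k = 5 | 86.5% | 88.1% | 89.7% | 92.8% |

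The unadjusted comparison has 87.6%. The effect therefore runs from a loss of 87.6 − 86.5 = 1.1 points to a gain of 93.3 − 87.6 = 5.7 points, and the assumed R² decides where in that range it falls. The half-width figures need no effect size, but they need R² just as much.

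**Step 3: do the documents say where R² lies?** They do not. They give no baseline pain score, no factor named as prognostic, no indication mix and no statement that indication was recorded before allocation. The pathologies in the Introduction describe what hysteroscopy is used for in general, not who was enrolled. The baseline variables shown to be available are eligibility criteria, and eligibility narrows them: age 18 to 65, ASA I or II, BMI from 18.5 to below 25 kg/m². A model with age and ASA class alone may explain next to nothing, and it would leave the variation between indications in the error term, which is the very thing that prompted the question.

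**Step 4: could a change still be made?** Covariates protect the result only if they are fixed before outcomes are seen by arm. The SAP says that data were analysed and that power was calculated retrospectively. That is not proof, since the past tense may be a habit of style and no unblinding date is given. It does make it likely that any adjusted model chosen now would be post hoc, with the t-test remaining the main analysis.

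**The case for a change.** The strongest counter-argument is that the trade is lopsided. If no covariate is prognostic, adjustment costs 0.5 to 1.1 power points at d = 0.512 (0.6 to 1.5 at d = 0.40; 0.2 to 0.6 at d = 0.60). If R² reaches 0.10, it gains roughly 2 to 3 points and narrows the interval by 3.5% to 4.5%. The break-even is also low. If indication alone mattered, with two, three or four equally common and evenly spaced levels, a gap of 0.29, 0.41 or 0.51 within-level SD between the extreme levels would be enough.

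The arithmetic stands, and as general advice to someone designing a similar trial it is sound. It does not turn the t-test into an error here. The favourable cases need a prognostic variable recorded before randomisation and chosen while allocation was still blinded, and the documents establish neither. Choosing an adjusted or an unadjusted main analysis under such uncertainty is a matter on which competent statisticians differ.

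**Conclusion.** The concern does not hold. The unadjusted t-test is a valid comparison of the arms at any single VAS time, and mixed indications without stratification do not undermine it: simulated type I error was 0.049 to 0.054. Adjustment is an alternative whose effect cannot be signed from the documents. It runs from about 1.1 power points lost to 5.7 gained for R² between 0 and 0.20 at the back-solved 0.512 SD. On the SAP's apparent timing, it would probably not alter the main analysis anyway.

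This rests on three assumptions: VAS is analysed under the SAP's rule for continuous variables, allocation was not stratified by indication (if it was, the test errs on the cautious side), and the R² range is illustrative. The conclusion covers only the absence of covariates. It does not settle which of the four VAS times is primary, how multiplicity across them is handled, or what happens if the normality check fails.
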